A single-center prospective randomized controlled pilot trial was conducted at the Presley Regional Trauma Center at Regional One Health in Memphis, TN from 1/1/16 to 12/13/17. This hospital is the only trauma center in Memphis, serves as the only trauma center in the Mid-South area, and is a major teaching facility for the University of Tennessee Health Science Center. The Mid-South is a geographic area of approximately 3,500 square miles surrounding Memphis including western Tennessee, eastern Arkansas, northern Mississippi, and small portions of Missouri and Kentucky. The trial is registered on clinicaltrials.gov (NCT02957331). After informed consent was obtained by one of the investigators or research nurses from the patient or legally authorized representative (LAR), patients were randomly assigned to either the treatment (PRO) or control arm using block randomization in groups of 4 to ensure equal group size. This sequence was generated using SAS version 9.4 (SAS Institute, Cary, NC). The study was not blinded due to the treatment effects and need for titration of the medication on physiologic parameters.

The primary outcome was in-hospital mortality. The secondary outcome was to examine the interaction between beta-blockade and catecholamines by measuring urinary catecholamines. A power analysis was performed using literature review to determine probable effect size. Utilizing a 15% difference in mortality between groups, a sample of 99 patients per group would be required to power the study at 0.80. This sample size would not be feasible at a single center. Therefore, in lieu of performing a multi-center study with limited resources, we elected to perform a pilot study to determine study

safety, feasibility, and effect size over a one-year period. The enrollment was re-assessed after one year and still short of the goal, so the study was extended an additional year.

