Eligible patients for screening were 18 years or older with a TBI as determined by Glasgow Coma Scale score (GCS) less than 12 on admission and documented brain injury on head computed tomography scan. Qualifying patients were randomized within 72 hours of injury. Exclusion criteria included patients with a significant injury in another body region (Abbreviated Injury **Scale score** >3), incarceration or gravidity, hepatic disease, home beta-blocker use, ongoing resuscitation or vasoactive medications, active acute coronary syndrome, and **non-survivable injury as determined by neurosurgery review of imaging**. Data were extracted from the electronic medical record (Sorian, Cerner, Kansas City, MO) and the local trauma registry (NTRACS version 3.0, Digital Innovations, [name]). Patients assigned to the PRO arm were dosed with propranolol starting at 20 mg three times daily (TID) by mouth or per feeding tube. The dose of propranolol was increased daily in 20 mg TID increments (60 mg/day total) until heart rate (HR) was less than 100 beats per minute (bpm) with maximum dose of 640 mg/day. Parameters for holding the medication included HR less than 60 bpm or systolic blood pressure less than 100 mm Hg. Patients assigned to the control arm were managed per institutional standard for TBI based on the Brain Trauma Foundation guidelines.²⁷ Neither arm had additional beta-blockers withheld if the care team deemed that class of medication necessary for appropriate care. Treatment duration for active study intervention was 14 days with a 48-hour taper of propranolol after the study period ended in the PRO arm. Patients were followed during the hospital stay until death or discharge.

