Variables collected included demographics, severity of injury, severity of illness scores, physiologic parameters, operative interventions, hospital length of stay (LOS), intensive care unit length of stay (ICU LOS), discharge disposition, infectious morbidity, urinary catecholamines, and mortality. Urinary catecholamines were collected from discarded urine at study enrollment and then at study day (SD) 2, SD-5, SD-7, SD-10, and at the end of the study period (SD-14) or when the patient came off study. The samples were stabilized with hydrochloric acid (HCl) and sent to a standard lab. Timely acid stabilization of the urine specimens was required prior to shipping to the central lab for processing. If HCl was not added to the specimen, unpredictable results were obtained that were not physiologically possible *in vivo*. These values were excluded from analysis. Patients in the PRO arm were compared to the control **using intent to treat analysis.**

Statistical analyses for categorical variables were compared using *Chi*-square tests or Fisher's exact tests where appropriate. Normally distributed continuous variables were compared using *Student's* t-tests and non-normally distributed continuous variables were compared using Wilcoxon Rank Sums tests. Effect size for mortality was calculated using the absolute difference between treatment groups. A two-way mixed model III Analysis of the Variance (ANOVA) with repeated measures was used to estimate differences between the two treatment arms over time. Using planned contrasts, the mean for each follow-up measurement was compared to SD-1 (i.e., randomization) for *within-group* contrasts and means at each assessment time were compared for *between-group* contrasts. Because these contrasts were planned, no correction was made for multiple comparisons. Output for the ANOVA is reported as Least Square Means

(LSMeans) with standard error (\pm SE). Finally, Kaplan-Meier survival analysis was performed to further examine mortality over time between groups. All statistical analyses were performed using SAS 9.4 (SAS Institute, Cary, NC). The University of Tennessee Health Science Center and Regional One Health Institutional Review Boards approved the study. A *p* value of less than 0.05 was considered significant.

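### Does the plan need a rule for deaths in the hospital and ICU length-of-stay comparison?

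*Combined protocol and SAP*

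**What the plan says.** The data-collection paragraph (unnumbered) lists "hospital length of stay (LOS), intensive care unit length of stay (ICU LOS") with demographics, severity scores, disposition and other variables. It gives no definition of stay. The design paragraph names in-hospital mortality as primary outcome and urinary catecholamines as secondary; stay is neither.

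Three general statements then apply to it:

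- Arms are compared by intent to treat: "Patients in the PRO arm were compared to the control".
- Continuous variables go to a t-test if normal; otherwise "non-normally distributed continuous variables were compared using Wilcoxon Rank Sums tests".
- Follow-up ends with either event: "Patients were followed during the hospital stay until death or discharge".

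Mortality gets its own treatment. "Effect size for mortality was calculated using the absolute difference between treatment groups", and "Kaplan-Meier survival analysis was performed to further examine mortality over time between groups". Nothing comparable is stated for stay: no survivor-only set, no worst-rank value for deaths, no free-days measure and no competing event.

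**The concern.** In-hospital death is the primary outcome and it also ends the stay. Put all randomised patients into a rank test with stay running to death or discharge, and a death on day 5 looks like a discharge on day 5. The power paragraph works from a 15-point mortality difference. If propranolol lowered mortality by that much and deaths came sooner than live discharges, the propranolol arm would tend to show a longer stay with no difference in recovery, so a beneficial treatment could look worse on this line. The pilot is meant to inform on safety, feasibility and effect size, so a later trial team might misread it.

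**Working it through.** **1. Inputs.** From the documents: a 15-point mortality difference, 99 per group, power 0.80, significance at 0.05. Not in the documents: control mortality, sidedness of the test, time to death, survivor stay and enrolled number. These are assumed below.

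**2. Mortality rates consistent with the plan's figure.** The plan says "a sample of 99 patients per group would be required to power the study at 0.80". The pooled two-proportion formula is

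n = [z(α/2)·√(2p̄q̄) + z(β)·√(p₁q₁ + p₂q₂)]² / (p₁ − p₂)².

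For 25% vs 10%, p̄ = 0.175: [1.960·√0.28875 + 0.8416·√0.2775]² / 0.0225 = (1.0532 + 0.4433)² / 0.0225 = 99.5. Other pairs also fit: 22% vs 7% (two-sided, continuity correction, 98.2), and one-sided 31% vs 16% (97.7), 32% vs 17% (100.6) and 27% vs 12% with correction (98.1). The figure is attainable, and the choice of pair barely moves the results.

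**3. Shift in median hospital stay.** Assume survivor stay is lognormal in both arms, median 18 days and log-SD 0.6, so treatment has no effect on stay. Enter deaths at their time of death. The arm median t solves

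p·F_D(t) + (1 − p)·F_S(t) = 0.5.

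Example, deaths at 3 days plus an exponential with total mean 12:

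- Control, p = 0.25, t = 15.8: 0.25·0.759 + 0.75·0.414 = 0.50.
- Propranolol, p = 0.10, t = 17.1: 0.10·0.792 + 0.90·0.468 = 0.50.
- Shift: 17.1 − 15.8 = 1.3 days.

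All six death-timing cases for 25% vs 10%, with simulated Wilcoxon rejection rates:

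| Deaths | Mean time to death (days) | Median shift (days) | Rejection, 25 per arm | Rejection, 99 per arm |
|---|---|---|---|---|
| From day 0 | 5 | 2.3 | 11% | 35% |
| From day 0 | 7 | 2.0 | 10% | 28% |
| From day 0 | 10 | 1.5 | 8% | 19% |
| None before day 3 | 12 | 1.3 | 7% | 15% |
| None before day 3 | 15 | 0.9 | 6% | 10% |
| None before day 3 | 18 | 0.6 | 5% | 7% |

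Across the other mortality pairs the shift reaches at most 2.5 days with early deaths and 1.4 with later ones. The highest rejection rates, over the four pairs tested (32% vs 17% was not), are 12% at 25 per arm and 36% at 99.

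**4. Which rows are plausible.** Randomisation could take place up to 72 hours after injury, and "non-survivable injury as determined by neurosurgery review of imaging" was an exclusion. An exponential with mean 5 from day 0 puts 1 − exp(−3/5) = 45% of deaths before day 3, which sits badly with both. The lower three rows fit better. The 99-per-arm column is a size the plan itself calls infeasible at one centre.

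**5. Shift against noise.** At 25 per arm the SD of the difference in medians is about 3.9 days. The later-death shifts are 0.6/3.9 = 0.15 to 1.4/3.9 = 0.36 SD; the largest early-death shift is 2.5/3.9 = 0.64 SD. For 25% vs 10%, propranolol shows the longer median in 56-72% of trials instead of 50%.

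**6. Sensitivity.** With survivor median 12-25 days and log-SD 0.4-0.8 the shift runs from −0.2 to +4.3 days. A separate simulation (survivor median 20 days, mortality 20% vs 5% or 30% vs 15%) gave rejection of 11-12% at 25 per arm for deaths at median 5 days, about 10% at 8 days, and 4-5% when deaths had the same stay distribution as survivors. For ICU stay (assumed survivor median 9 days, all deaths in the ICU) the shift runs from +0.8 to −0.5 days, so even its sign is open.

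**7. The alternative.** Take a cumulative-incidence curve of live discharge with death as the competing event. By day 28 the proportion discharged alive is (1 − p)·Φ(ln(28/18)/0.6) = (1 − p)·0.769, that is 0.90·0.769 = 69% vs 0.75·0.769 = 58%. At 25 per arm the 95% half-width is 1.96·√[(0.69·0.31 + 0.58·0.42)/25] = 0.265, about 27 points around an 11-point gap. With equal survivor stay, a log-rank test on this curve would reject in 24% of trials at 25 per arm, on mortality alone, against 5-12% for the Wilcoxon test.

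**The case for a change.** The strongest case for a change is that the omission can be verified, works through the primary outcome and costs a sentence or two to close from data already collected. A survivor-only summary would not escape it: that too would be an unstated rule, and it conditions on a post-randomisation event.

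The omission and the mechanism stand. Three things do not carry through. First, the text does not say that a death counts as a completed stay; that is one reading of general statements, and a survivor-only summary is not excluded. Second, days to death or discharge for everyone randomised is a coherent description of bed use. It misleads only if read as recovery time, and the plan nowhere presents it so. Third, the remedies have the same weakness: a split by vital status conditions on survival, and the live-discharge curve carries more of the mortality difference than the test it would replace.

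**Conclusion.** No change to the plan follows. The missing rule is a detail that analysts ordinarily settle when they report stay: they say how deaths were counted and set the figures beside mortality. In the better-fitting death-timing cases the Wilcoxon test at 25 per arm rejects in 5-7% of trials against 5% nominal, and the median moves by 0.6-1.4 days, well inside the sampling noise. With early deaths it is 8-12% and 1.5-2.5 days, still under one SD. These sizes rest on assumed death times, survivor stays, mortality rates and arm size, none of which the documents give, and under some inputs the sign reverses. The mortality and catecholamine conclusions do not depend on the point. Fuller methods for stay would be a trade-off, with no gain for any conclusion the pilot is set up to draw.

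### Does the shared last urine slot (study day 14, or whenever the patient left the study) spoil the final catecholamine contrast?

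*Combined protocol and SAP*

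**What the plan says.** The document has no section numbers, so places are given by topic.

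- Outcomes paragraph: "The secondary outcome was to examine the interaction between beta-blockade and catecholamines by measuring urinary catecholamines". The primary outcome is in-hospital mortality.
- Variables paragraph: urine was "collected from discarded urine at study enrollment and then at study day (SD) 2, SD-5, SD-7, SD-10", and finally "at the end of the study period (SD-14) or when the patient came off study". The only stated rule on sample handling drops specimens that were not acid-stabilized.
- Statistical paragraph: a repeated-measures ANOVA "was used to estimate differences between the two treatment arms over time". Within each arm "the mean for each follow-up measurement was compared to SD-1"; between arms "means at each assessment time were compared for" the second set of contrasts. The outcome of this model is not named.
- Treatment paragraph: "Treatment duration for active study intervention was 14 days", and "Patients were followed during the hospital stay until death or discharge".

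**The concern.** Every collection but the last has a single defined time. The last has two: day 14, or an earlier day that varies by patient. What counts as coming off study is not defined, and no rule maps those samples to the time factor. Follow-up stops at death or discharge in patients with brain injury and a GCS below 12, so exits before day 14 are foreseeable, and the schedule itself allows for them.

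If the off-study samples were all put in the day-14 level and catecholamines change over time, two things follow. The last within-arm contrast would no longer estimate the change to the end of treatment, even with the same pattern of exits in both arms. The last between-arm contrast could be biased, but only if the share, timing or type of exits differs by arm. At stake is one time point of the only stated secondary outcome.

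**Working it through.** The plan has no figure of its own on this point. Its 99 per group belongs to the mortality power calculation and serves below only as an upper limit for n. Below, σ is the standard deviation of the measurement; day 1 and day 14 are the plan's SD-1 and SD-14.

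**What the text settles.** It settles when urine was taken. It does not say whether an off-study sample is coded to day 14, to its own day, to the nearest scheduled day, or to a separate level. That the ANOVA was fitted to catecholamines is also an inference, though a likely one given the sampling schedule. The calculation therefore rests on two unstated steps.

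**Inputs.**

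- From the document: days 1 and 14, hence a span of 13 days.
- Assumed: share of leavers f, their mean day d, a linear fall of 1σ from day 1 to day 14, and correlation 0.5 between two samples of one patient.
- Patients per arm: 25 (assumed) to 99. The number enrolled is not given.

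**Shift of the final level if merged.** Shift = f × (14 − d)/13 × fall.

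- f = 10%, d = 11: 0.1 × 3/13 = 0.023σ
- f = 30%, d = 8: 0.3 × 6/13 = 0.138σ, so a fall of 1σ reads 0.862σ
- f = 50%, d = 5: 0.5 × 9/13 = 0.346σ
- Arm difference, d = 8, 30% in both arms: 0
- Arm difference, d = 8, 20% against 40%: 0.2 × 6/13 = 0.092σ

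**Against sampling error.** The within-arm standard error is √(2 × 0.5/n): 0.200σ at n = 25 and 0.101σ at n = 99. The between-arm standard error is √(2/n): 0.283σ and 0.142σ.

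- Within arm: 0.138/0.200 = 0.7 standard errors at n = 25, and 0.138/0.101 = 1.4 at n = 99
- Between arms: 0.092/0.283 = 0.3, and 0.092/0.142 = 0.65

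The n = 99 end is doubtful, because the plan itself calls that size infeasible at one center.

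**Shape of the trend.** Keep a total fall of 1σ, 30% leavers and exit days uniform on 3 to 13. An exponential decline with a half-life of 2 to 6 days gives a within-arm shift of 0.04σ to 0.10σ, and 0.03σ to 0.07σ between arms at 20% against 40%. A linear fall that is complete by day 7 gives 0.05σ and 0.03σ. An early fall thus shrinks the effect; other shapes could enlarge it.

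**What recoding would gain.** Take n = 25, a fall of 1σ and 30% leavers.

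- No departures: z = 1/0.200 = 5.0
- Merged coding: z = 0.862/0.200 = 4.3
- Only patients with both samples: 0.7 × 25 = 17.5 patients, standard error √(1/17.5) = 0.239σ, z = 1/0.239 = 4.2

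The ratio to full data is 0.862 against √0.7 = 0.837, whatever the fall or n. At f = 10% it is 0.977 against √0.9 = 0.949. At f = 50% it is 0.654 against √0.5 = 0.707, so strict coding wins only there. A mixed model that borrows leavers' earlier samples would lose somewhat less than the paired figures.

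**Departures linked to prognosis.** These are simulated results from a random-intercept model with 300,000 per arm. Patients who die sit 0.5σ high throughout and those discharged 0.5σ low; 30% leave each arm, and deaths are 1/3 of leavers in one arm and 2/3 in the other. Merged coding gives falls of 0.86 and 0.86, an arm difference of about 0. Scheduled-day coding gives 0.98 and 1.02, a difference of −0.04σ; repeat runs gave −0.02σ to −0.03σ.

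**The case for a change.** The best case for acting is this. The within-arm distortion needs no imbalance between arms. Early exits are certain enough that the schedule provides for them. Two analysts could code the same samples differently, and both would be following the text. The contrasts are tested at 0.05 without multiplicity correction, so each is read alone. Writing a coding rule costs almost nothing if sample dates were recorded.

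Most of the factual part stands: neither the definition nor the coding rule is there, and someone reading the final within-arm estimate would need to know which days it covers. In some settings recoding is also better. With exits unrelated to prognosis at 20% against 40%, the simulated arm difference is 0.09σ merged and 0.00 by scheduled day. If all leavers die at those same shares, it is 0.09σ against about −0.045σ.

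What does not stand is the step from a missing sentence to a wrong analysis. The secondary question concerns beta-blockade and catecholamines, which is mainly a comparison of arms, and there the error is zero unless exits differ. The larger figure belongs to the uncontrolled change within an arm. Neither coding dominates: scheduled-day coding is the worse of the two between arms when equal numbers leave for different reasons. A day-14 contrast in patients still on study, or a further model in continuous time, answers a different question rather than repairing this one. Reporting within-patient change looks clean in the simulation (1.00 in both arms), but only because each patient's offset was assumed constant.

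**Conclusion.** No change to the plan follows. The wording leaves a real but small gap: the plan gives collection times and leaves the coding of off-study samples to the analyst, who can use the sample day or treat the last slot as an end-of-participation value. Pooling into day 14 is possible but not stated, and neither is the use of this ANOVA for catecholamines.

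If both were done, the illustrative within-arm error is 0.02σ to 0.35σ, with 0.14σ at 30% leaving at mean day 8. The between-arm error is 0 for equal departures and 0.09σ at 20% against 40%. These sizes rest on an assumed linear fall of 1σ and assumed departures; the document gives no departure figures, so the trial's own error cannot be computed. At 30% leavers, the test of the within-arm fall is about as strong merged (z = 4.3) as in complete pairs (z = 4.2), and no changed conclusion has been shown. The more elaborate alternatives are a trade-off, with a possible shift in the arm difference of roughly 0.02σ to 0.04σ when departures follow prognosis. The matter is confined to one time point of a secondary outcome in a pilot trial and does not touch the mortality analysis.

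### Within-arm tests against SD-1 have the same standing as the between-arm contrasts, and no arm-by-time test is named for the catecholamine outcome

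*Combined protocol and SAP*

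**What the plan says.** The design and outcomes paragraph (unnumbered) of the combined protocol and SAP states: "The secondary outcome was to examine the interaction between beta-blockade and catecholamines by measuring urinary catecholamines". It gives no analyte, time point or statistical definition.

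The data collection paragraph schedules urine samples "at study enrollment and then at study day (SD) 2, SD-5, SD-7, SD-10, and at the end of the study period (SD-14", or at the time a patient came off study. That is one baseline and five follow-up times.

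The statistical analysis paragraph specifies a two-way mixed-model ANOVA that "with repeated measures was used to estimate differences between the two treatment arms over time". It does not name the outcome. That the model is for the catecholamines is an inference from the matching study-day schedule. One sentence then lists two sets of contrasts:

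- within-group: "the mean for each follow-up measurement was compared to SD-1 (i.e., randomization" for this set;
- between-group: "means at each assessment time were compared for" this set.

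On multiplicity the paragraph says: "Because these contrasts were planned, no correction was made for multiple comparisons". The one significance rule for all analyses is that a p "value of less than 0.05 was considered significant". The ANOVA output is to be least-squares means with standard errors.

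**The concern.** The two sets of contrasts answer different questions. A between-arm contrast compares randomized groups. A within-arm contrast against SD-1 asks only whether that arm changed. Patients enter within 72 hours of injury and are followed to SD-14, so both arms could plausibly change with no drug effect at all.

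The plan puts no order between the sets. Most of the listed tests are within-arm, they use the same 0.05 threshold, and nothing says which result answers the secondary outcome. That leaves room to report a significant fall in PRO alongside a non-significant fall in control as an effect of propranolol. A difference in significance between arms is not a significant difference between arms. The quantities that would show the latter directly, an arm-by-time test or a between-arm difference in change from SD-1, are not named. Least-squares means with SE by arm do not supply the standard error of a difference in change.

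At stake is the conclusion on the secondary outcome. The primary outcome, mortality, is untouched.

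**Working it through.** **The plan's own figures.** The documents give no figure for the catecholamine analysis. The 99 per group relates to mortality, its control rate is not stated, and it does not bear on this point.

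**Count of contrasts per analyte**, from the sampling schedule and the contrast sentence:

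- within-arm: 5 follow-ups × 2 arms = 10;
- between-arm: 6 assessment times = 6, of which 5 fall after enrollment;
- between-arm difference in change from SD-1, or arm-by-time: 0 named.

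**One day, closed form.** Suppose both arms have the same true change and each within-arm test has power *p*. The arms are independent, so

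- P(significant in PRO only) = *p*(1−*p*), at most 25%;
- P(significant in exactly one arm) = 2*p*(1−*p*), at most 50%, reached at *p* = 0.5.

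At *p* = 0.2 or 0.8 the second is 2 × 0.2 × 0.8 = 32%. At *p* = 0.9 it is 18%. The problem is largest at intermediate power, which small samples tend to give.

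**One day, simulated.** No drug effect, same true change in both arms, correlation with baseline assumed 0.5, 5,000 trials per row:

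| n per arm | Change (SD) | Significant in one arm only | Between-arm test of change | Between-arm test at follow-up |
|---|---|---|---|---|
| 15 | 0.5 | 49% | 5.4% | 4.9% |
| 25 | 0.5 | 45% | 5.7% | 5.0% |
| 50 | 0.3 | 49% | 5.3% | 5.0% |
| 50 | 0.8 | 0% | 4.8% | 5.0% |

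The last row shows that the discordance vanishes when both arms are almost sure to be significant.

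**Five follow-up days, simulated.** Assumptions, none of them from the documents: 13-25 per arm, decline 0.3-0.7 SD, correlation 0.9^days, complete data, and paired t-tests standing in for the model contrasts. The decline is immediate, linear, or exponential with a 3-day constant. Over that grid:

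- significant fall in PRO but not in control, on at least one day: about 20-58% of trials;
- significance in one arm only, either direction, on at least one day: about 44-91%;
- between-arm test of change, and between-arm contrast at follow-up: each near 5% per day.

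The shape of the decline matters. With 20 per arm and a 0.5 SD decline, either-direction discordance on at least one day is about 74% (linear), 84% (immediate) and 90% (exponential). On SD-2 alone, under the immediate drop, it is 0.7%.

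The any-day percentages should not be set against a per-day 5%. A like-for-like yardstick is at least one false positive among the five post-enrollment between-arm contrasts: 1 − 0.95^5 = 22.6% if they were independent, and less if they are positively correlated. Most of the excess in the within-arm reading remains, but at the bottom of the PRO-only range there is little or none.

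**Precision of the alternatives.** With equal variances, the between-arm difference at follow-up has variance 2σ²/n and the difference in change has 4σ²(1−ρ)/n. Their ratio is 2(1−ρ). For the difference adjusted for the SD-1 value, the ratio to the follow-up comparison is 1−ρ². With the assumed ρ = 0.9^(days since SD-1):

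| Day | ρ | Change: 2(1−ρ) | Adjusted: 1−ρ² |
|---|---|---|---|
| SD-2 | 0.90 | 0.20 | 0.19 |
| SD-5 | 0.66 | 0.69 | 0.57 |
| SD-7 | 0.53 | 0.94 | 0.72 |
| SD-10 | 0.39 | 1.23 | 0.85 |
| SD-14 | 0.25 | 1.49 | 0.94 |

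The raw difference in change is less precise than the contrast already planned once ρ falls below 0.5. The adjusted difference is not.

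**The case against.** The strongest reply is that the plan already contains the right kind of comparison. The same sentence that lists the within-arm contrasts lists between-arm contrasts at each assessment time, the stated aim of the model is the difference between arms over time, and PRO is compared with control by intention to treat. This stands. A reader who stops halfway through the sentence might infer that the plan tests each arm separately and has no randomized comparison of catecholamines. The documents do not support that.

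A reader might also infer that the secondary outcome is by definition an arm-by-time interaction and that the analysis omits it. That goes too far on both counts. The interaction named is between a drug and an analyte and may be meant biologically. A two-way model in arm and time would also ordinarily contain the arm-by-time term. What can be said is that the term is neither named as a test nor listed for reporting.

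Nor do the documents say that a fall in PRO only will be taken as a drug effect. The plan invites that reading by giving both sets equal standing, but it does not commit to it. The simulated percentages measure how often the opportunity would arise, under assumed arm sizes, declines and correlations.

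Finally, this is an exploratory outcome in a self-described pilot. That lowers the weight of the point. It does not remove it: a pilot meant in part to learn about effect size is best served by a between-arm estimate with an interval.

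**Conclusion.** The point holds in a limited form. The plan gives ten non-randomized within-arm tests per analyte the same threshold and standing as six between-arm contrasts, does not say which set answers the secondary outcome, and names no arm-by-time test or between-arm difference in change. The between-arm contrasts are sound, so the fault lies in the standing given to the within-arm p-values and in the unnamed test.

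With no drug effect, a PRO-only fall on at least one day would be available to report in about 20-58% of trials, and discordance in either direction in about 44-91%. These ranges rest wholly on the assumed arm size, decline, correlation and shape of the decline. The application to catecholamines rests on the study-day schedule. Severity is modest.

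**What to change.** 1. Report within-arm changes from SD-1 as descriptive, without p-values.
2. State that the ANOVA is for the urinary catecholamines, if that is so, and name the arm-by-time interaction from that model as the analysis of the secondary outcome. Keep SD-1 as a level of time for this test. Without it, a constant difference from SD-2 onward would sit in the arm main effect and be missed.
3. Report the between-arm difference with a 95% CI at each of the five follow-up days, alongside the least-squares means. Preferably adjust it for the SD-1 value, for example in a companion fit with the follow-up days as responses and SD-1 as covariate, because the raw difference in change loses precision when the correlation with SD-1 is below 0.5.

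The cost is a few sentences in the analysis text and a few ESTIMATE or CONTRAST statements, plus the companion fit if adjustment is chosen. No new data are needed. Fewer results will be called significant. The text is written in the past tense, so if results have already been seen, the report should say that the test was designated afterwards.

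### If the repeated-measures ANOVA is the urinary catecholamine analysis, its five post-enrollment between-arm contrasts have no stated baseline adjustment and are read at p<0.05 uncorrected because they were planned

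*Combined protocol and SAP*

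**What the plan says.** All references are to the combined protocol and SAP, whose sections are unnumbered.

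- **Sampling** (variables paragraph): "Urinary catecholamines were collected from discarded urine at study enrollment and then at study day (SD) 2, SD-5, SD-7, SD-10", with a last sample "at the end of the study period (SD-14) or when the patient came off study". That is six times, five of them after enrollment. Specimens that were not acid-stabilized gave impossible results: "These values were excluded from analysis".
- **Model** (statistical analysis paragraph): a two-way mixed-model repeated-measures ANOVA "was used to estimate differences between the two treatment arms over time". No outcome is named for it.
- **Within-arm contrasts**: "the mean for each follow-up measurement was compared to SD-1 (i.e., randomization").
- **Between-arm contrasts**: "means at each assessment time were compared for" these. No baseline covariate and no between-arm comparison of change from SD-1 is stated.
- **Threshold and multiplicity**: a p "value of less than 0.05 was considered significant", and "Because these contrasts were planned, no correction was made for multiple comparisons".

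The design paragraph makes urinary catecholamines the secondary outcome and calls the trial a pilot. The analytes are not listed, and no day or overall test is named as the deciding one.

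**The concern.** Two things follow if this ANOVA is the catecholamine analysis.

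First, the reason given for not correcting does not support the decision. Specifying contrasts in advance guards against picking them after seeing the data. It does not limit the chance that one of five tests is positive by luck. A reader who sees one significant day for one analyte has no stated rule for how much weight to give it, because the contrasts are not labelled exploratory.

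Second, the between-arm contrasts appear to give up precision that is already available. Each patient's enrollment value is collected and is used for within-arm change, which does not compare the arms. No use of it is stated in the comparison that does. In a pilot whose enrollment was still short of its goal after one year, that information is worth having.

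**Working it through.** The documents give no error rate or precision figure for this analysis, so there is none to reproduce. The 99 patients per group concerns mortality and does not bear on this point.

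**1. Count of contrasts.** There are six sampling times. Treating the enrollment sample as SD-1, which the text implies but does not say outright, leaves five between-arm contrasts per analyte that can reflect the drug. A sixth, at SD-1, would compare randomized arms at baseline and is not a test of drug effect.

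**2. False-positive rate per analyte.** Inputs: threshold 0.05 (from the plan), two-sided (assumed), no drug effect, correlation r between contrasts (assumed; the documents give none). If the contrasts are independent, the rate is 1 − 0.95^5 = 22.6%. Otherwise, simulate z_j = √r·u + √(1−r)·e_j for j = 1 to 5, with u and e_j standard normal, and count draws in which any |z_j| > 1.96 (400,000 draws). With correlation that decays over time (AR(1)) at 0.3, 0.5, 0.7 and 0.9, the rates are 21.7%, 20.0%, 17.3% and 11.8%, inside the same range.

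**3. Precision from the enrollment value.** Assumptions: exchangeable known covariance with correlation ρ between any two samples from one patient, SD-1 mean shared by the arms, and 20% of enrollment specimens unusable at random. For one follow-up day with complete follow-up, the variance relative to no baseline use is

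1 / [0.8/(1 − ρ²) + 0.2].

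- ρ = 0.3: 1/(0.8/0.91 + 0.2) = 0.927
- ρ = 0.5: 1/(0.8/0.75 + 0.2) = 0.789
- ρ = 0.7: 1/(0.8/0.51 + 0.2) = 0.565

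Generalized least squares with all five follow-up days in the model gives 0.925, 0.782 and 0.550 for a single day.

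**4. The two effects side by side.** Under this covariance with complete follow-up, the correlation between unadjusted contrasts equals ρ, so the two columns move together.

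| Assumed correlation | At least one false difference, five contrasts | Single-day variance with SD-1 constrained |
|---|---|---|
| 0 | 22.6% | 100% |
| 0.3 | 21.0% | 92% |
| 0.5 | 18.3% | 78% |
| 0.7 | 14.9% | 55% |
| 0.9 | 10.1% | not computed |

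**5. Missing follow-up.** A likelihood mixed model with SD-1 in the response already borrows from it when later samples are missing, so the constraint then adds less. At ρ = 0.5, the constrained model's single-day variance relative to the unconstrained model is 78% with complete follow-up, 83% with 30% of follow-up samples missing and 87% with 50% missing (missing completely at random).

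**The case against.** The case for leaving the plan alone is substantial. The ANOVA's outcome is not named, and physiologic parameters were also collected and could be its subject. The outcome is secondary, the trial is a pilot, and the absence of correction is openly disclosed. Means are reported with standard errors, so readers can judge for themselves. A two-way ANOVA would ordinarily also yield overall arm and arm-by-time tests, though none is designated. Whether to correct such contrasts is a trade-off. All of this stands, and it keeps the point small. It does not rescue planning as a reason, and it does not explain the absence of a baseline adjustment.

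A reader might infer more than the documents support:

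- **That the enrollment value is not used at all.** It is the reference for every within-arm contrast. Only the between-arm contrasts lack a stated use of it.
- **That one analyte in four would mislead.** That needs six contrasts and near-zero correlation (1 − 0.95^6 = 26.5%), and it counts the SD-1 comparison, which cannot show a false drug effect. Five contrasts never exceed 23%.
- **That both problems are at their worst together.** The table shows that they move in opposite directions.
- **That the between-arm contrasts are biased for want of adjustment.** Randomization protects them on that score; the loss is in precision. Samples lost to exclusion, death or discharge are a separate matter, which adjustment does not settle.
- **That baseline adjustment is free.** The documents do not say that the enrollment urine preceded the first dose.

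**Conclusion.** The point holds as a modest one, on the condition that the ANOVA is the catecholamine analysis. The SD-1 label and the wording about follow-up measurements fit the urine schedule, the only serial schedule given, but this remains an inference.

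On that reading, the uncorrected per-day contrasts carry a 10% to 23% chance per analyte of at least one false between-arm difference, for assumed correlations of 0.9 to 0. The number of analytes is not stated, so no rate across analytes can be fixed. The unused precision is worth a reduction of single-day variance to about 92%, 78% or 55% at assumed ρ of 0.3, 0.5 or 0.7 with 20% of baselines missing. The reduction is to about 87% at ρ = 0.5 if half the follow-up is also missing, and there is none at ρ = 0. The clearest improvement is the baseline constraint, since it uses data already collected; formal correction is optional. Nothing here touches the mortality analysis.

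**What to change.** 1. Name the outcome of the repeated-measures ANOVA and list the analytes.
2. Keep the mixed model with SD-1 in the response, and constrain its mean to be equal across arms. This also removes the SD-1 between-arm test.
3. Remove planning as the reason for no correction, and label the per-day catecholamine contrasts exploratory. If only one sentence can change, it should be this label.
4. Confirm that the enrollment specimen precedes the first propranolol dose, and report usable samples by arm and day.

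**Cost.** A model statement and a few sentences; no new data. The model rests on the timing in item 4 and on missing samples being missing at random. The latter is a strong assumption, because some samples are lost to death, which is the primary outcome. Enrollment is described as finished, so the revised analysis must be labelled post hoc and cannot restore prospective error control. The constraint improves precision but does not correct for multiplicity, which is why the label is still needed.

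**Optional.** One overall test per analyte of the average difference over follow-up, and Holm on the five days. Holm alone holds the per-analyte rate at 4.9% to 2.4% (correlations 0 to 0.9). A one-day effect with 80% unadjusted power has 59% under Holm, and the average test would find it only 9% to 24% of the time. If all five days share such an effect, the average test has 83% to 100% power. Reading the average test and Holm side by side gives 5.0% to 8.7% false claims per analyte, not 5%.
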